Cover Page for Clinical Trial Study

Official Title: The Effect of Animal-Assisted Therapy on Prosocial Behavior in Children with Developmental Delay or Autism Spectrum Disorder

NCT #: N/A

Date: November 11, 2024

Study Protocol

Clinical Study Description

The purpose of this study is to investigate the effect of animal-assisted therapy (AAT) on prosocial behavior and emotional regulation, both during and after AAT sessions, in children referred for an autism spectrum disorder (ASD) evaluation or documented developmental delay (DD) or behavioral concerns. We seek to address identified gaps in knowledge of the use of canines in therapy sessions by analyzing short- and long-term effects of AAT and human-animal interaction occurring in AAT sessions. Caregivers were given the option to enroll the child in the AAT study at the follow-up appointment after the diagnostic assessment was completed, or upon enrollment in the ASD program if the child had an ASD diagnosis. Each AAT study lasted between eight to 12 weeks, and caregivers had the option to re-enroll the child for the next study to continue addressing behavioral concerns. Animal-assisted therapy sessions lasted 30 to 45 minutes, depending on the age and ability of the participant. Sessions started with five to 10 minutes of free play with the canine, followed by sensory integration therapy based on the child's identified sensory profile. Participants then entered the clinic room for 20 to 30 minutes of a seated activity in which the therapist, a certified pediatric nurse practitioner (CPNP), taught coping and socialization strategies to participants and caregivers. Sessions concluded with five minutes of play with the canine. Play activities include fetch, soccer, hide and seek, and puzzles. The canine was trained to lay under the table in the clinic room while the therapist was working with the participants. He would provide grounding, light pressure, and deep pressure therapy if the participant became anxious during the sessions. The seated work was recorded using two cameras to ensure visibility of the interactions between the participant and therapist, canine, and caregiver; participant vocalizations and verbalizations; and participant facial expressions. We used two human-animal ethograms to code behavior during sessions and two behavioral assessments to note behavior occurring after sessions. All sessions occurred in the clinic located on the university's campus. Demographic data including participant age, gender, race, ethnicity, referral source, prior medical diagnoses, age of ASD or DD diagnosis, medications, and prior allied health, school, or psychological evaluations. The canine was trained as a therapy dog and was being trained as a service dog at the time of the study. The canine was present during sessions to interact with children and assist them to practice and develop skills to address identified deficits in social-emotional and adaptive functioning, prosocial behavior, and emotional regulation. AAT sessions were recorded to code interactions at a later time.

Objectives

1. Do interactions between a trained therapy canine and autistic children differ depending on the child's verbal abilities?
2. Is there a difference in prosocial behavior and emotional regulation in AAT sessions among children with varying verbal abilities?
3. Is there a difference in prosocial behavior and emotional regulation apart from animal-assisted therapy sessions among children with varying verbal abilities?

Design

We used standardized instruments to investigate human-animal intervention (HAI) occurring during AAT sessions and prosocial behavior and emotional regulation demonstrated by participants outside of AAT sessions. SPSS and Microsoft Excel were used to run the analysis. Descriptive statistics were utilized to compare prosocial behavior and emotional regulation occurring apart from AAT sessions between the two groups based on the self-report questionnaires completed by caregivers. Independent t-tests were used to analyze the differences in human-animal interaction among children with ASD with varying verbal abilities from the recorded sessions. The homogeneity of the variance (HOV) assumption between two groups was checked using Levene's test for equality of variances in SPSS program before conducting the t-tests analysis. Results of t-tests with adjusted degrees of freedom value were reported if the HOV was violated. The null hypothesis was set to reflect no significant difference in HAI between verbal and nonverbal groups for the independent t-tests; therefore, a significant difference in the human-animal interaction behaviors regarding the children's verbal abilities could be confirmed if the t-test results reject the null hypothesis. Cohen's d was used to report the effect sizes of the independent t-tests; values up to 0.20 were interpreted as small, 0.50 as medium, and 0.80 as large effect sizes.

Methods

Demographic data; past, family, and social histories; and prior therapy evaluations were collected during the initial consultation for enrollment into the ASD program.

The Observation for Human Canine Interaction for Research (OHAIRE) Coding System from University of Arizona was used to note human bonding and prosocial behavior occurring during AAT sessions. The OHAIRE Coding System was specifically created for use in research with participants aged 4 to 16 years but may also be suitable for individuals of other ages, provided appropriate validity and reliability analyses are conducted. Participants must be with at least one other person during sessions to allow for the coding of social behaviors. The participant being observed is known as the primary participant. The coding system allows for the primary participant to engage in social behaviors with various targets, including caregivers, therapists, objects, and canines. While the OHAIRE was designed to code behavior in the presence of common domesticated canine species, it has been tested with a restricted range of canine species to date. The tool has previously been used to code interactions with dogs and guinea pigs, as well as social behaviors before and after interactions with horses (not direct interactions with horses). The coded behaviors are general enough to be assumed to apply to other domesticated canine species. Participants were video recorded continuously during unstructured interaction opportunities. Available activities provided opportunities to engage in both social and isolated behaviors. The video sample included a wide enough angle to observe the environment and all potential social interaction partners. The OHAIRE-V3 calculates a human-canine bond score in order to quantify the interactions taking place between the primary participant and the canine. The human-canine bond score was calculated for each 10-second interval based on the presence of an interaction between the primary participant and the canine, and the type of behaviors shown during that interaction. Participants received one point for each of the six behaviors from the 'social communication & interaction' category in the OHAIRE tool. No points were given if the primary participant does not interact with the canine. The behaviors included in the definition of the human canine bond score are talk, gesture, look, touch, affection, and prosocial behavior directed toward the canine. There are a total of six 10-second intervals within each 1-minute video segment, and each of those 10-second intervals has six possible points: one point for each type of interaction. The total score from each 10-second interval is summed for a total overall human-canine bond score across the entire 1-minute video segment. Each 10-second interval will have a score between 0 and 6 points. Each 1-minute video segment will have a score between 0 and 36 points.

The 3-AAT Observation ethogram, adapted with permission from Johns Hopkins University, was used to code both canine and human interaction during AAT sessions. The revised ethogram appraises the frequency of six domains of human interaction (affection, play, care, communication, comfort, withdrawal) and 24 subdomains of human behavior that can occur in an AAT session as seen in Table 1. The ethogram assesses the frequency, intensity, and duration of the interactions between the canine and child. Frequency is measured by a tally count and duration is assessed by rounding either up or down to the nearest 30 second mark. Each interaction has a code for intensity from 0 (not intense) to 3 (the most intense), and the mode of the interaction was entered to run the analysis.

The Strengths and Difficulties Questionnaire (SDQ) is a 25-item tool developed to assess five domains: Emotional Problems, Conduct Problems, Hyperactivity, Peer Problems, and Prosocial. The SDQ is the most used instrument in measuring therapeutic effect of interventions within the emotional state in children and adolescents ages 2 to 18 years, demonstrating reliable internal consistency and validity. The SDQ has two versions, one to be administered at the initiation of therapy and then a follow-up version that includes two additional questions examining the impact of the therapeutic intervention. Scores from four behavioral domains range from zero ("normal") to 10 ("very high concerns"), while Prosocial domain scores are reversed so that 10 indicates "normal" behavior and zero signifies "very high concerns". The SDQ also assesses the total, impact, internalizing, and externalizing scores to provide a complete overview of the child's behavior during the past four weeks. Total scores are the sum of the behavior domains except the Prosocial domains and range from zero (normal) to 40 (very high). Impact scores range from zero (normal) to 10 (very high) and reflect overall distress and impairment interfering with daily social interactions. Internalizing scores reflect the Emotional Problems and Peer Problems domains, while Externalizing scores are the sum of the Conduct Problems and Hyperactivity domains. Both the Internalizing and Externalizing domain scores range from zero (normal) to 20 (very high). The initial SDQ was administered at the beginning of the study and the follow-up assessment was used subsequently every four weeks until the study concluded.

Lastly, the Positive and Negative Affect Schedule (PANAS) was administered weekly to measure therapeutic effects occurring in everyday life outside of the AAT session. The PANAS is a 20-item questionnaire utilizing a 5-point Likert scale to assess positive and negative affect occurring the week prior to administration. Each domain has 10 items with scores ranging from 10 to 50, with lower scores reflecting lower levels of positive or negative affect and higher scores signifying higher positive or negative affect²⁹. Total scores on each scale are obtained by adding the scores for each item. Analysis of the PANAS demonstrates very good internal consistency reliability, with alphas ranging from 0.86 to 0.90 for Positive affect and from 0.84 to 0.87 for Negative affect.

Statistical Analysis Plan

This present study used standardized instruments to investigate human-animal interaction (HAI) occurring during AAT sessions and prosocial behavior and emotional regulation demonstrated by participants outside of AAT sessions. SPSS and Microsoft Excel were used to run the analysis. Descriptive statistics were utilized to compare prosocial behavior and emotional regulation occurring apart from AAT sessions between the two groups based on the self-report questionnaires completed by caregivers. A total of 144 sessions were conducted, 84 of which were recorded and coded to analyze HAI during sessions. Independent t-tests were used to analyze the differences in human-animal interaction among children with ASD with varying verbal abilities from the recorded sessions. The homogeneity of the variance (HOV) assumption between two groups was checked using Levene's test for equality of variances in SPSS program before conducting the t-tests analysis. Results of t-tests with adjusted degrees of freedom value were reported if the HOV was violated. The null hypothesis was set to reflect no significant difference in HAI between verbal and nonverbal groups for the independent t-tests; therefore, a significant difference in the human-animal interaction behaviors regarding the children's verbal abilities could be confirmed if the t-test results reject the null hypothesis. Cohen's d was used to report the effect sizes of the independent t-tests; values up to 0.20 were interpreted as small, 0.50 as medium, and 0.80 as large effect size.

Protocol Number: 2201382953
Investigator: [name]

Expiration Date: 03/31/2024
Last Approval Date: 04/01/2023

University of Arkansas System

Document Overview

Description: Animal-Assisted Therapy in Autism Care Management
Explanation:
Organization Doc Num:

Protocol Summary

Protocol Number: 2201382953
Sequence Number: 6
Status: Active - Open to Enrollment
Expiration Date: 03/31/2024
Last Approval Date: 04/01/2023
Investigator: [name]

Protocol Details

Type: Expedited
Summary/Keywords:
Application Date: 02/07/2023
Reference ID1:
Reference ID2:
FDA Application No:
Title: The Effect of Animal-Assisted Therapy on Prosocial Behavior in Children with Developmental Delay or Autism Spectrum Disorder

Areas of Research

Code	Description
000001	All Research Areas

Organizations

Type	Organization	Address
Performing Organization	University of Arkansas	University of Arkansas [name]

Funding Source

Type	Number/Code	Source	Title
Internally Funded/ Unfunded Research	unfunded	N/A	

Protocol Number: 2201382953
Investigator: [name]

Expiration Date: 03/31/2024
Last Approval Date: 04/01/2023

Subjects

Subject	Count
Children	20
Adults	40

Investigators

Person Name: [name] **Role:** Principal Investigator
Units: CC012723 UAF | NURS | Department of **Affiliation:** Supervisor
Nursing
Office [contact] **Mobile:**
Email: [contact]

Person Name: [name] **Role:** Co-Investigator
Units: CC012702 UAF | PSYC | Psychology **Affiliation:** Supervisor
Office [contact] **Mobile:**
Email: [contact]

Study Personnel

Person Name	Role	Affiliation	Email
[name]	Study Personnel	Student Investigator	[contact]
[name]	Study Personnel	Student Investigator	[contact]
[name]	Study Personnel	Student Investigator	[contact]
[name]	Study Personnel	Student Investigator	[contact]
[name]	Study Personnel	Student Investigator	[contact]
[name]	Study Personnel	Student Investigator	[contact]
[name]	Study Personnel	Student Investigator	[contact]
[name]	Study Personnel	Student Investigator	[contact]
[name]	Study Personnel	Student Investigator	[contact]
[name]	Study Personnel	Student Investigator	[contact]
[name]	Study Personnel	Student Investigator	[contact]

Questionnaire

Questionnaire Name: Human Subjects Protocol Interview
Description: Human Subjects Protocol Interview
Module: IRB **Sub Module:**
Protocol Number: 2201382953 **Sequence Number:** 6
Principal Investigator: [name]
Title: The Effect of Animal-Assisted Therapy on Prosocial Behavior in Children with Developmental Delay or Autism Spectrum Disorder

- **What is the purpose of this research? Please explain both why you are doing the research (class assignment, thesis, etc.) AND/OR state your hypothesis. See attachment is not a sufficient response.**

The proposed project will investigate the effects of utilizing animal-assisted therapy (AAT) in the therapy plan for youth with autism spectrum disorder (ASD) or developmental delay (DD). The purpose of this study is to explore identified gaps in knowledge pertaining to AAT in pediatric ASD and DD care management. Specifically, we seek to document canine care and behavior during training and AAT sessions, assess human and canine interaction during AAT sessions, and analyze long-term effects of AAT on social-emotional and adaptive functioning in the pediatric participants once the sessions have ended. This study will address the following research questions: 1. What measures should be taken to ensure protection of the canine before, during, and after AAT sessions as well as during training? 2. What human-animal interaction behaviors are present during AAT sessions with pediatric participants ages 12 months to 18 years? 3. What effect does AAT have on pediatric development and social-emotional and adaptive functioning? 4. Are effects in development and social-emotional and adaptive functioning produced by AAT sustainable after completion of the 12-week AAT program?

- **Are you collecting data about living individuals?**

Yes

- **Are you collecting data through intervention or interaction with these individuals?**

Yes

- **Beyond the basic Participant Types (children, UofA Students, adults, etc.) named elsewhere in this application, do you have a target population (particular group of people) you want to recruit? Some examples might be students in a particular class, members of a particular group or network, people in a specific age range (whether adult or minor), children in a particular school or class, etc.**

Yes

- **Describe your target population.**

[name] collaborates with the Community Clinic of NWA who refer children, ages 18 months to 18 years, at risk for developmental delay or autism spectrum disorders to her clinic, Access for Autism (A4A), for further developmental evaluation and care management. Children receiving care management by the A4A program who have developmental or behavioral concerns can volunteer to enter this study.

- **How are you recruiting participants? Are you standing in a public place asking people to take a survey, sending out introductory emails, posting an ad or blurb on a website or social media, posting a flyer in a public location, etc.? **Please note that all recruitment materials will need to be uploaded in the Notes and Attachments section.**

[name] will discuss the study with parents/guardians whose children have been referred to the A4A clinic for further developmental evaluation. Participation in the study is voluntary and does not affect other services provided by the A4A clinic.

- **Provide a brief description of the procedures involving the participants.**

All interactions between the canine and participants will occur either at the A4A clinic, in the EPLEY Center for Healthcare Professionals, or at the Psychology lab on campus. The first interaction between the canine and the participant will focus on introducing the two and facilitating a bond through play, such as petting or brushing the canine, or throwing a ball. The Purdue University Veterinary College of Medicine O'HAIRE Coding System will be used to observe and code human behavior during this session. Drs. [name] and [name] use a variety of behavioral and developmental evaluations to identify concerns and provide strategies for home therapy to improve delays: 1. Participants ages 8 years and older who are cognitively capable will be asked to self-report their emotional state before and after each AAT session using an 11-point Likert scale chart in the shape of a thermometer, with ranges from "no distress/totally relaxed" to "highest anxiety/stress that you've ever felt." 2. Strengths and Difficulties Questionnaire 3. Positive and Negative Affect Schedule 4. Ages and Stages Questionnaire- 3rd edition 5. Ages and Stages Questionnaire: Social and Emotional - 2nd edition 6. Social-Emotional Assessment Measure 7. Vineland- 3rd edition 8. Social Responsiveness Scale- 2nd edition 9. PEDS: DM-AL 10. Stanford-Binet Intelligence Quota Test Caregiver satisfaction and perspectives of AAT integration in therapy sessions will be assessed via surveys. Demographic data including participant age, gender, race/ethnicity, referral source, prior medical diagnoses, age of ASD or DD diagnosis, medications, and prior allied health or psychological therapies will be collected on all participants. [name] will incorporate AAT into the therapy sessions at the A4A clinic that are guided by the Ages and Stages developmental and social/emotional assessments to target gross and fine motor skill, language, social, and emotional development. Parents will be given handouts that are designed to address deficits identified by the ASQ-3, ASQ:SE-2, and SEAM assessments. The canine will be present to interact with children as they are learning their skill for that week. For example, the canine will interact with the participant while the participant is learning a new skill, such as improvement in handwriting, and the participant will be able to interact and play with the canine if the participant focuses on completing the therapy assignment. Likewise, participants will earn points if they perform their therapy strategies at home and can use those points to interact and play with the canine at their next therapy session. Plush dog toys who look like the canine will be given to pediatric participants as incentive to perform their home therapies. The following data will be collected on the canine: 1. The Canine Behavioral Assessment and Research Questionnaire (C-BARQ), a validated measure to quantify animal behavior during training developed by the University of Pennsylvania in 2003. The C-BARQ database will be used to compare the canine's training progress with other Black Labrador Retriever dogs and can also alert to the onset of behavioral problems so [name] can target these concerns early in the training process. 2. The canine behavior ethogram which assesses 26 canine behaviors during human-animal interactions. The ethogram is divided into three categories: affiliative indicators, moderate stress indicators, and high-stress indicators. The research team will track the number of AAT sessions in which the canine participates each day to assess for variations in temperament and performance. 3. The exact minutes in which canine behaviors are present will be recorded in each AAT session, noting patterns that indicate fatigue or distress. Human-animal interaction will be assessed by: 1. The Purdue University Veterinary College of Medicine O'HAIRE Coding System will be used to observe and code human behavior during AAT sessions. Observable behaviors categories captured by the OHAIRE Coding System include Interactive Behaviors (Social Communication & Environmental Interaction), Emotional Display (Facial, Verbal), and Interfering Behaviors (Aggression, Overactivity, Isolation). The OHAIRE-V3 assessment will be used to calculate a human-animal bond score to quantify the interactions taking place between the pediatric participants and the animal. The ELAN Coding software will be used to achieve high inter-rater reliability through precise timing of observed interactions. All AAT sessions will be recorded after receiving consent from families to retroactively code participant behavior during sessions.

- **How long are the procedures likely to take? Include duration and frequency.**

The A4A weekly therapy sessions will last about 30 minutes; however only it is expected that the total HAI time will be approximately 10-15 minutes, depending on the therapy activity. Honors students will assist the canine with [name] during the sessions and will take the canine to [name] office once the HAI part of the appointment has ended.

- **How will information be given to people to get their informed consent to participate in this research? Answers should include specific methods (e.g., verbal consent, information handout, online consent form, full consent form requiring signature documentation.) **Please note that consent materials -- from a script for verbal consent to full consent forms that require participant signature -- must be uploaded in the Notes and Attachments section.**

[name] will contact parents/guardians of potential participants to explain the AAT program and gauge their interest. If interested, parents will come to the A4A clinic on the first floor of ECHP to meet the canine and sign the informed consent form. Verbal assent will be obtained from pediatric patients who are cognitively able to give it.

- **Does data collection rely on a scheduled event, such as a convention or specific date?**

No

- **How will your data be collected? Include all that apply: online, on paper/in person, audio and/or video recordings. **Please note that all data collection materials will need to be uploaded in the Notes and Attachments section. This includes: surveys, questionnaires, interview questions or anything that is given to or asked of a participant.**

Data will be collected in the initial consultation form for the A4A clinic, through performing developmental assessments, and with surveys. All AAT sessions will be recorded after receiving consent from families to retroactively code participant behavior during sessions. The following will be used to collect data: 1. A4A Intake form: all participants 2. Ages and Stages Questionnaire- 3rd edition: 1 month to 5.5 years 3. Ages and Stages Questionnaire: Social/Emotional- 2nd edition: birth to age 6 years 4. Social and Emotional Assessment/ Measure: 2 to 66 months 5. Strengths and Difficulties Questionnaire: 3 to 16 years 6. Positive and Negative Affect Schedule: 9 to 14 years 7. Vineland- 3rd edition: 3 to 21 years 8. Social Responsiveness Scale- 2nd edition: 2.5 to 18 years 9. PEDS: DM-AL: 7 to 11 years 10. Stanford-Binet IQ Test: 2 to 18 years

- **How will your data be stored? Include all that apply: electronically, on paper, audio and/or video recordings.**

Survey data will be stored in REDCap, a HIPAA-secured software which caregivers of youth with complete on a personal device (iPad, laptop, cellphone). Data will only be accessible by approved research staff. Data obtained in the ASQ- 3, ASQ: SE-2, SEAM, Vineland- 3, Strengths and Difficulties Questionnaire, and the Positive and Negative Affect Schedule scores will be stored in [name] password protected laptop. Any hard-copy measures of documents will be stored in Drs. [name] or [name]'s locked lab space in a locked filing cabinet. Video files will be downloaded from camcorders directly to [name] locked lab space located in Memorial Hall on the password-protected computers and then additionally secured as a password protected file. Only authorized research personnel will have access to these files.

- **How will that data be kept secure?**

Data will be stored on Drs. [name] and [name]'s password-protected computers. Any hard-copy measures of documents will be stored in [name] locked lab space in a locked filing cabinet. Only participant numbered IDs will be included on assessment documents. Participant identifying information and associated ID numbers will be stored in the [name] lab in a password protected computer on a password protected document. Only Drs. [name] and [name] will have access to participant ID information while the remaining research staff will utilize participant ID numbers. All video files will be downloaded to Dr.

[name]'s lab computers within 24 hours and then immediately deleted from the camcorder device. Video files will be stored on a password-protected computer as password-protected documents.

- **Minimal Risk is defined as risks of harm not greater than those ordinarily encountered in daily life or during the performance of routine physical or psychological examinations or tests. Will participants be exposed to more than minimal risk? Include in your consideration the potential of mental risks if asking sensitive questions, or legal or reputational risks in case of breach of confidentiality.**

Yes

- **Describe the risks in question and any precautions that will be taken to minimize those risks.**

Participants will not be exposed to more than minimal risks while receiving developmental or behavioral evaluations. Participants will be exposed to the canine during therapy sessions for approximately 10 to 15 minutes weekly. The canine will be removed if signs of fatigue, fright, or irritation appear. He will remain on leash throughout the entire AAT session and will be wearing a harness. Honors students will have the canine's leash during the AAT session and will hold him by the harness handle. Also, [name] will assess the disposition of the pediatric participants before allowing the canine to come to the room and will not allow the canine to participate if the pediatric participant's behavior is disruptive or potentially dangerous for the canine.

- **Are there any direct benefits to the participants for participating in this study?**

Yes

- **Describe the benefits participants will or may receive.**

Pediatric participants will receive one plush toy that looks like the canine they are working with.

- **Will the proposed research involve deception or the withholding of information from participants?**

No

- **Will the proposed research necessitate medical clearance from a physician prior to participation?**

No

- **Will the proposed research involve gathering biological samples (blood, tissue, etc.)?**

No

- **Will the proposed research involve administering of substances or providing food and drink, other than water, to participants?**

No

- **Will the proposed research involve physical exercise or conditioning?**

No

- **Does the research require review by a non-UofA IRB?**

No

- **Does this research require approval from another institution or agency, such as a school or privately owned business?**

No

Protocol Number: 2201382953

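### The verbal/nonverbal contrast is not shown to be prespecified yet is worded as confirmable, while the stated question, the effect of AAT, has no matching analysis

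*Combined protocol and SAP*

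**What the plan says.** **Approved record.** The Human Subjects Protocol Interview (application dated 02/07/2023, last approval 04/01/2023) sets out four research questions under its purpose item. The first concerns the dog's welfare: "What measures should be taken to ensure protection of the canine before, during, and after AAT sessions as well as during training". The second asks which behaviours between child and dog occur in sessions, for participants from 12 months to 18 years old. The third is the question of effect: "What effect does AAT have on pediatric development and social-emotional and adaptive functioning". The fourth asks whether any such effects last once the 12-week programme is over.

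Its procedures item numbers ten child evaluations, among them "2. Strengths and Difficulties Questionnaire 3. Positive and Negative Affect Schedule 4. Ages and Stages Questionnaire- 3rd edition". Its data-collection item gives a second list of ten, with age ranges, which includes "Vineland- 3rd edition: 3 to 21 years 8. Social Responsiveness Scale- 2nd edition: 2.5 to 18 years". OHAIRE coding is approved in the same procedures item, outside the numbered list.

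**2024 text.** The cover date is November 11, 2024, and the text is in the past tense. The Clinical Study Description gives the purpose as the effect of AAT on prosocial behaviour and emotional regulation, in the short and long term. It says that two ethograms and two behavioural assessments were used. All three Objectives compare children by verbal ability; the second reads "Is there a difference in prosocial behavior and emotional regulation in AAT sessions among children with varying verbal abilities". Under Methods, the SDQ is given at the start and every four weeks, and the PANAS weekly. The Statistical Analysis Plan reports: "A total of 144 sessions were conducted, 84 of which were recorded and coded to analyze HAI during sessions". Independent t-tests compare human-animal interaction (HAI) between verbal and nonverbal children. Design and the Statistical Analysis Plan both say that rejecting the null would confirm a difference. The caregiver questionnaires are compared between the two groups by descriptive statistics only.

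**The concern.** A p-value supports confirmatory language only if the contrast, the grouping and the outcomes were fixed before the data could inform them. Here the contrast is missing from the approved questions and appears in a text that already reports the final session counts. Nothing labels it exploratory. A reader would take a rejected null as confirmation of a planned hypothesis.

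The second difficulty concerns what is left unanswered. The study says that it investigates the effect of AAT, and approved questions 3 and 4 ask about that effect and whether it lasts. No planned analysis estimates change in a child over the course of AAT. Most of the numbered evaluations also disappear without comment. A reader cannot tell whether they showed nothing, were never repeated, or served only to guide therapy.

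**Working it through.** The plan states no sample-size, power or alpha figure, so there is nothing of that kind to reproduce. The check is a side-by-side reading with counts.

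**1. Questions against objectives.** Approved questions that compare children by verbal ability: 0 of 4. Current objectives that do: 3 of 3. In the interview, the word verbal occurs only for an OHAIRE display category and in connection with consent and assent. The available text gives no definition, instrument or cut-off for verbal versus nonverbal.

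**2. Timing.** The application is dated 02/07/2023. The Objectives stand in a text dated November 11, 2024, which reports 144 sessions held and 84 coded (84/144 = 58%). This dates the text. It does not date the decision to make the comparison.

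**3. Which objective the confirmatory sentence serves.** The sentence concerns HAI, so it belongs to Objective 1. No separate test is named for Objective 2. Objective 3 is descriptive only.

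**4. Measures against analyses.** The Statistical Analysis Plan names neither questionnaire. The Methods text identifies the caregiver questionnaires as the SDQ and PANAS.

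| List | Not analysed |
|---|---|
| Ten numbered evaluations, procedures item | 8 of 10: distress thermometer, ASQ-3, ASQ:SE-2, SEAM, Vineland-3, SRS-2, PEDS: DM-AL, Stanford-Binet |
| Ten items, data-collection item (intake form in place of thermometer) | 8 of 10 |
| Procedures list plus OHAIRE (approved and used) | 8 of 11 |
| Procedures list plus OHAIRE and caregiver satisfaction survey | 9 of 12 |

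**5. Purpose against analyses.** SDQ and PANAS bear on the social-emotional part of question 3, but only as a description of two groups. No analysis estimates change with AAT. No adaptive-functioning measure such as the Vineland-3 is analysed, although questions 3 and 4 name that domain.

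**6. What repeated data should exist.** At four-weekly intervals, a study of 8 to 12 weeks gives 8/4 = 2 to 12/4 = 3 SDQ follow-ups per child, and weekly PANAS gives about 8 to 12 scores. Within-child change can therefore be computed for both.

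**7. Why the wording matters.** The 3-AAT ethogram has six domains and 24 subdomains, scored for frequency, intensity and duration. No primary outcome or multiplicity rule is stated. Assuming alpha 0.05 and all nulls true, 6 tests give 6 × 0.05 = 0.3 expected false rejections, and 24 × 3 = 72 tests give 72 × 0.05 = 3.6. The number of tests actually run is not stated, so this is a range and not an estimate.

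**The case against.** The strongest reply is that a late write-up does not prove a late decision. Only sequence 6 of the approved protocol is shown, and one part of the combined document, just before the committee review entry, was not available for this check. A dated amendment could exist. This stands. A reader might infer that the contrast was chosen after seeing the data, but the documents do not establish that. The remedy must therefore depend on what the sponsor can show.

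The second reply is that the ten evaluations are partly clinical tools. The interview introduces them as ways to identify concerns and plan home therapy, and the ASQ-3, ASQ:SE-2 and SEAM generate handouts for parents. No section calls any of them an endpoint. Only the thermometer, SDQ and PANAS have a stated repeat schedule. This also stands, so a reader who infers that approved endpoints were selectively withheld goes further than the text. Against it, the data-collection item lists nine of the ten (all but the thermometer) as sources of study data, so their fate should still be stated.

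Third, the sentence about confirmation may be only a clumsy account of what rejecting a null means. That is possible, but it appears twice and nothing nearby marks the comparison as exploratory.

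Fourth, age limits and small numbers may make change estimates uninformative. The data-collection item gives 3 to 16 years for the SDQ and 9 to 14 for the PANAS, and the approved count is 20 children. This limits precision. It does not excuse leaving the study's own question without an estimate.

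**Conclusion.** The concern holds in this form: the verbal/nonverbal contrast is not shown to be prespecified, and its confirmatory wording for HAI is unsupported on the record available. Separately, the stated purpose and approved questions 3 and 4 have no matching analysis, and 8 of the ten numbered evaluations are not analysed.

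Two further readings should be avoided. Question 3 is not wholly uncovered, because SDQ and PANAS touch its social-emotional part; what is missing is an estimate of change. Nor does the plan offer a confirmatory test of Objective 2 or Objective 3.

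The conclusion rests on two assumptions: that the caregiver questionnaires are the SDQ and PANAS, as the Methods text indicates, and that no unavailable record dates the contrast before coding. Such a record would remove the objection to its timing. It would not supply the missing analysis of change.

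**What to change.** 1. In Design and in the Statistical Analysis Plan, replace the sentence on confirmation with exploratory wording, unless a dated record shows that the contrast was set before coding. In either case, state when it was set.

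2. Add one table of within-child change from the first score, with 95% confidence intervals, for the SDQ and PANAS and for any other listed measure that was repeated. Label it as uncontrolled change, because there is no comparison without AAT. For children who re-enrolled, say which score counts as the first.

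3. For the remaining listed measures, give only the number of children with a first score and with a repeat score. State which were not collected and which served only to guide therapy.

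**Cost.** Revised wording and one table, with no new data collection. The verbal/nonverbal claim becomes exploratory. Some intervals will be wide: if all 20 approved children had a repeat score, the half-width would be 2.093/√20 = 0.47 standard deviations of change; with 10 it would be 2.262/√10 = 0.72. The SDQ schedule stops when the study concludes, so the table bears on question 3. It bears on question 4 only if scores exist from after the sessions ended; if none do, the report should say that sustainability was not assessed.
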